Suspicion for graft versus host disease (GVHD): If there is a concern for GVHD, then we recommend consideration of a biopsy for diagnostic work-up if clinically appropriate. Evidence of grade III or higher acute GVHD would be considered a DLT (except for skin GVHD, must have at least stage 3 involvement to be a DLT) as this often triggers systemic corticosteroids. These patients would stop receiving study treatment (both ipilimumab and decitabine), and followed for up to 1 year after treatment for AE resolution, response and survival. Those with skin GVHD that is overall grade II with stage 1-2 involvement or less will be able to stay on study. Topical corticosteroids are allowed. For GVHD events that are less than grade III, ipilimumab dose can be skipped (decitabine can continue) until event resolution or when the event is controlled without requiring systemic corticosteroids or immunosuppressive agents (exception: topical steroids) (missed ipilimumab doses will not be made up); these patients may remain on study. Please see [Appendix B](#) for resources to be used for acute and chronic GVHD grading.

It is necessary to delay ipilimumab dosing for the following related adverse events:

- Any \geq Grade 2 non-skin related adverse event (including immune related AE (irAEs)), except for asymptomatic laboratory abnormalities, grade 2-3 fatigue, and grade 2 anorexia (as the latter two events can be caused by disease alone). Treatment does not need to be delayed for controlled (on treatment) or recently treated infections.
- Any \geq Grade 3 non-hematologic laboratory abnormality except for grade 3 fatigue (as can be caused by disease). Treatment does not need to be delayed for controlled (on treatment) or recently treated infections.
- Any adverse event, laboratory abnormality or intercurrent illness that, in the judgment of the investigator, presents a substantial clinical risk to the subject with continued dosing
- Any \geq Grade 3 skin related adverse event (unless considered to be related to underlying disease, leukemia cutis, or a drug-allergy that is not due to study drug (ie antibiotics))
- An event that is not considered to be necessarily related to ipilimumab but requires a brief course of corticosteroid therapy.
 - An example, if a patient develops Sweet's syndrome (febrile neutrophilic dermatosis, confirmed by skin biopsy), then prednisone would be warranted. Patients would be allowed to continue decitabine to maintain disease control.

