Patients should be informed of and carefully monitored for evidence of clinically significant systemic immune-mediated adverse reactions (e.g., systemic lupus erythematosus-like diseases) or organ-specific immune-mediated adverse reaction (e.g., rash, colitis, uveitis, hepatitis or thyroid disease). If an immune-mediated adverse reaction is noted, appropriate work-up (including biopsy if possible) should be performed, and steroid therapy may be considered if clinically necessary.

It is unknown if systemic corticosteroid therapy has an attenuating effect on ipilimumab activity. However, clinical anti-tumor responses have been maintained in patients treated with corticosteroids and discontinued from ipilimumab. If utilized, corticosteroid therapy should be individualized for each patient. Prior experience suggests that colitis manifested as \geq grade 3 diarrhea requires corticosteroid treatment.

Suggested guidelines for specific immune-mediated adverse reactions are included in [section 6.4](#) below, in [Appendix C](#), and the package insert. These suggested guidelines should be utilized as clinically appropriate for the treatment of individual patients. Please contact the overall PI or drug monitor for any questions.

Overview of Management of Immune Related AE

Immune related AE include dermatologic, gastrointestinal, hepatic, endocrine and other less common inflammatory events that resolve from general immunologic enhancement. Temporary

immunosuppression with corticosteroids, tumor necrosis factor-alpha antagonists, mycophenolate mofetil, or other agents can be effective treatment in most cases.

For patients with moderate or severe immune related AE, this requires interruption of the ipilimumab and the use of corticosteroid immunosuppression. Treatment is based upon the severity of the observed toxicity:

- For patients with grade 2 (moderate) immune-mediated toxicities, treatment with ipilimumab should be withheld and should not be resumed until symptoms or toxicity is grade 1 or less. Corticosteroids (prednisone 0.5 mg/kg/day or equivalent) should be started if symptoms do not resolve within a week.
- For patients experiencing grade 3 or 4 (severe or life-threatening) immune-mediated toxicities, treatment with ipilimumab should be permanently discontinued. High doses of corticosteroids (prednisone 1 to 2 mg/kg/day or equivalent) should be given. When symptoms subside to grade 1 or less, steroids can be gradually tapered over at least one month.

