6.4.2 Immune-mediated Hepatitis and Pancreatitis

Hepatic immune-related AEs were mostly clinically silent and manifested as transaminase or bilirubin laboratory abnormalities. Fatal hepatic failure has been reported in clinical trials of ipilimumab. **Serum transaminase and bilirubin and lipase levels must be evaluated before each dose of ipilimumab as early laboratory changes may be indicative of emerging immune-related hepatitis/ pancreatitis and elevations in liver function tests (LFTs) may develop in the absence of clinical symptoms.** Increase in LFT or total bilirubin should be evaluated to exclude other causes of hepatic injury, including infections, disease progression, or other medications, and monitored until resolution. Liver biopsies from patients who had immune-related hepatotoxicity showed evidence of acute inflammation (neutrophils, lymphocytes, and macrophages).

Monitor liver function tests (hepatic transaminase and bilirubin levels, lipase) and assess patients for signs and symptoms of hepatotoxicity/ pancreatitis before each dose of ipilimumab. In patients with hepatotoxicity, rule out infectious or malignant causes and increase frequency of liver function test monitoring until resolution. Withhold ipilimumab in patients with grade 2 hepatotoxicity.

Permanently discontinue ipilimumab in patients with grade 3–5 hepatotoxicity/pancreatitis and administer systemic corticosteroids at a dose of 1 to 2 mg/kg/day of prednisone or equivalent. When liver function tests show sustained improvement or return to baseline, initiate corticosteroid tapering and continue to taper over 1 month. Across the clinical development program for ipilimumab, mycophenolate treatment has been administered in patients who have persistent severe hepatitis despite high-dose corticosteroids.

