APPENDIX F ADVERSE EVENT GUIDANCE AND PRE TREATMENT CRITERIA CHECKLIST

(Note: this is not all inclusive for all visits, but for general study visit only)

- Clinic Visit
- Physical exam
- ECOG score
- Medication review
- Adverse event evaluation and grading if appropriate
- Immune-related adverse event evaluation:
 - Immediately alert Overall PI (required) if there is concern for cardiac toxicity at any time during treatment including clinical signs or concerns for heart failure, myocardial infarction, cardiomyopathy, or myositis. If there is concern for this, obtain at minimum CPK and troponin, cardiology consult, and EKG and echocardiogram, if it is clinically relevant. Please refer to section 6.4.7 for guidance on cardiac toxicity management for ipilimumab.
 - Prior to initiating treatment, always assess stool frequency (bowel movements per 24 hours).
 - Change in bowel habits (colitis)?
 - Blood in the stool, abdominal pain (colitis)?
 - Headache, especially frontal (hypophysitis)?
 - Unusual fatigue, impaired libido (hypophysitis)?
 - Cough, dyspnea (pneumonitis)?
- Labs including minimum of complete blood counts with differential and comprehensive metabolic panel
- Additional immune related labs every 3 months including: gamma GT, direct bilirubin, LDH, TSH and lipase
- If due for ipilimumab: LFTs must be reviewed and must be:
 - $\leq 3.0 \times$ institutional ULN for AST and ALT
 - $\leq 1.5 \times$ institutional ULN for total bilirubin
 - If elevated total bilirubin is due Gilbert's disease or disease-related hemolysis then total bilirubin $\leq 3.0 \times$ institutional ULN
 - If, during the course of treatment abnormal LFT values are detected, ipilimumab should not be administered. The subject should be evaluated and recommendations for management are in section 6 of the protocol with helpful algorithms in [Appendix C](#), as clinically appropriate.

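### For silent grade 2 liver-test elevations, section 6.2 does not require an ipilimumab delay, sections 6.2.2 and 6.4.2 withhold the dose, and Appendix F does not define its abnormal values

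*Combined protocol and SAP*

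**What the plan says.** Four places in the protocol bear on whether a scheduled ipilimumab dose is given when liver tests are raised without symptoms.

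- **Section 6.2, mandatory-delay list.** The list covers related events. Its first bullet requires delay for non-skin events of grade 2 or higher, immune-related events included, "except for asymptomatic laboratory abnormalities, grade 2-3 fatigue, and grade 2 anorexia". The second requires delay for non-hematologic laboratory abnormalities from grade 3 upward. The third applies at any grade: "Any adverse event, laboratory abnormality or intercurrent illness that, in the judgment of the investigator, presents a substantial clinical risk to the subject".
- **Section 6.2.2, overview of immune-related events.** "For patients with grade 2 (moderate) immune-mediated toxicities, treatment with ipilimumab should be withheld", and dosing does not resume until grade 1 or less.
- **Section 6.4.2.** "Hepatic immune-related AEs were mostly clinically silent and manifested as transaminase or bilirubin laboratory abnormalities". The rules are "Withhold ipilimumab in patients with grade 2 hepatotoxicity" and, above that, "Permanently discontinue ipilimumab in patients with grade 3–5 hepatotoxicity/pancreatitis".
- **Appendix F, pre-treatment checklist.** Before an ipilimumab dose, AST and ALT must be at or below 3.0 x ULN. Total bilirubin must be at or below 1.5 x ULN, or 3.0 x ULN with Gilbert's disease or disease-related hemolysis. These repeat the entry limits in section 3.1.8. The checklist then adds: "If, during the course of treatment abnormal LFT values are detected, ipilimumab should not be administered".

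I found no statement of which passage prevails.

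**The concern.** Section 6.4.2 says that hepatic immune-related events usually appear as laboratory changes without symptoms. The exemption in section 6.2 is for laboratory changes without symptoms. The exemption therefore covers the typical presentation for which 6.4.2 withholds the drug at grade 2. Two sites following the same protocol could treat the same patient differently, each with a passage to cite.

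This is a patient-safety matter first. It also bears on the primary endpoint, because the MTD or RP2D is set from cohorts of three to six patients per dose level and arm. If a held dose depends on the passage a site follows, patients counted at one dose level may have received different amounts of ipilimumab within the DLT window.

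**Working it through.** The plan gives no figure to reproduce here. The check sets the rules side by side for a silent elevation related to ipilimumab.

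| Elevation | 6.2 delay list | 6.2.2 and 6.4.2 | Appendix F numeric limits | Appendix F closing sentence |
|---|---|---|---|---|
| Grade 1, above ULN, within the Appendix F limits | No delay required unless judged a substantial risk | No withhold rule | Dose allowed | Barred if abnormal means above ULN; allowed if it means outside the limits |
| Grade 2 | No delay required unless judged a substantial risk | Withhold | Barred if above 3.0 x ULN (AST, ALT) or above the bilirubin limit | Barred if abnormal means above ULN; otherwise as the limits |
| Grade 3 or higher | Delay required | Discontinue permanently | Barred if above the limits | As above |

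**Grade 2.** The delay list and sections 6.2.2 and 6.4.2 give different answers. This is where the conflict lies.

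**Grade 1.** The only doubt is inside Appendix F. A patient with ALT at 2 x ULN meets the entry limit and the pre-dose limit, yet is barred if the closing sentence is read literally.

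**Grade 3 or higher.** No passage lets the scheduled dose go ahead as a matter of course. How the permanent-stop thresholds fit together is a separate matter.

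**Sensitivity to the grade cut-off.** The documents do not print liver-test grades as multiples of ULN, so the boundary is an assumption.

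- If grade 2 AST/ALT starts above 3.0 x ULN, a silent ALT of 4 x ULN (taken as still grade 2) is withheld by 6.4.2 and barred by the Appendix F limit. The delay list does not require a delay.
- If grade 2 starts lower, values between that point and 3.0 x ULN are withheld by 6.4.2. The Appendix F limit allows them and the delay list does not require a delay.

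The conflict between 6.2 and 6.4.2 at grade 2 remains either way. The same reasoning holds for bilirubin with its own limits.

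**Resumption.** Section 6.2 requires the event to return to grade 1 or less, or to baseline. The hepatotoxicity footnote in Appendix C resumes on return to grade 2, provided protocol-specific retreatment criteria are met. That proviso may bring it back to the 6.2 rule, but the text does not say so.

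**Doses affected in the DLT window.** The window is 56 days, or two 28-day cycles (section 5.2). The calendar in section 10.1 places ipilimumab on day 1 of cycles 1 and 2. An event related to ipilimumab cannot precede the first dose, so only the cycle 2 day 1 dose is at issue. Section 13.1 makes a patient non-evaluable only if cycle 1 is not completed for a reason other than DLT. A patient held at cycle 2 day 1 therefore still counts, having had one dose instead of two.

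**Frequency.** Section 2.2 offers two figures, neither from this combination.

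- Monotherapy at 10 mg/kg in melanoma: liver immune-related events 8.0% in total, 0.9% grade 1-2 and 6.8% grade 3-4. Applied to the maximum of 48 patients, 0.9% is 0.009 x 48 = 0.4 patients.
- 10 mg/kg plus dacarbazine: treatment-related ALT increases 29.1% and AST increases 26.7%, any grade. Applied to 48 patients, these are 0.291 x 48 = 14.0 and 0.267 x 48 = 12.8.

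The first counts diagnosed immune-related events. The second counts all grades with a partner drug for which the protocol itself reports more hepatic events than expected. Neither isolates silent grade 2 values, and the gap between them is too wide to support one estimate.

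**The case against.** The best defence is that the passages can be read together. The delay list says when a delay is compulsory, and an exemption from one of its bullets is not an order to dose. A reader might infer that section 6.2 directs the dose to be given. It does not: the investigator-judgment bullet remains, and the other sections add their own holds. On a cumulative reading, a patient above the Appendix F limits is simply held. That stands against the stronger inference. It does not remove the conflict, because section 6.2 says delay decisions must rest on specified safety criteria and then writes an express exception. The judgment bullet also needs a substantial risk, which 6.4.2 and Appendix F do not.

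A reader might also infer that Appendix F bars dosing at any value above ULN. Its closing sentence follows directly on the numeric limits and can well mean values outside them. The literal reading would empty those limits, including the Gilbert's and hemolysis allowance, of effect. The documents support only that the term is undefined.

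The texts differ in force: section 6.2.2 describes the immune-event management as suggested guidelines, and a calendar footnote calls Appendix F a helpful checklist. This has some weight, but the Appendix F limits are worded as requirements.

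Finally, a silent grade 2 value is not itself a DLT, since non-hematologic DLTs generally start at grade 3 (section 5.2), and adverse events are recorded whichever hold rule a site follows. Both points are correct and limit the statistical consequence to exposure.

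**Conclusion.** The inconsistency is real but narrow. For silent grade 2 liver-test elevations related to ipilimumab, section 6.2 does not require the delay that sections 6.2.2 and 6.4.2 call for, and Appendix F leaves the meaning of abnormal open. Within the DLT window it can change one dose per affected patient, at cycle 2 day 1; later doses can also be affected.

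The conflict between 6.2 and 6.4.2 does not depend on where grade 2 begins in multiples of ULN. Which side the Appendix F limits fall on does, and that cut-off is assumed. A reader might infer from the dacarbazine trial that about a quarter of patients are affected. The documents do not support this: those rates are any-grade and come from another combination, while the monotherapy table shows 0.9% low-grade liver events. The frequency in this trial is unknown. The passages should be corrected because they bear on safety and on comparable exposure within small cohorts.

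**What to change.** Reconcile the section 6.2 delay list, the section 6.2.2 overview, section 6.4.2 and Appendix F so that one consistent hold rule applies to AST, ALT and bilirubin, with its thresholds stated in one form. In the same revision:

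- say whether the exemption for asymptomatic laboratory abnormalities covers liver tests;
- define abnormal liver values in the closing Appendix F sentence;
- align the resumption wording in section 6.2 with the hepatotoxicity footnote in Appendix C.

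The choice of threshold belongs to the sponsor and investigators, and this review does not say which is right. The cost is wording only. Liver tests are already part of the day 1 chemistry for every cycle in section 10.1, so no visit, sample or patient is added.

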6.2.1 Exceptions to Permanent Discontinuation

- Potentially reversible inflammation (< grade 4), attributable to a local anti-tumor reaction and a potential therapeutic response. This includes inflammatory reactions at sites of tumor resections or in draining lymph nodes, or at sites suspicious for, but not diagnostic of metastasis.
- Hospitalization for neutropenic fever evaluation (this is a common adverse event of underlying disease and of decitabine).
- Hospitalization for \leq grade 2 adverse events where the primary reason for hospitalization is to expedite the clinical work-up.
- Patients with the following conditions where in the investigator's opinion continuing study drug administration is justified based on the potential for continued clinical benefit:

- Patients treated with systemic steroids for less than 4 weeks without evidence of autoimmune disease requiring steroids treatment
- Grade 2 skin rash treated with topical steroids for less than 4 weeks
- Grade 2 Ocular toxicity that has completely responded to topical therapy within 4 weeks
- Endocrinopathies where clinical symptoms are controlled with appropriate hormone replacement therapy. **Note:** Ipilimumab may not be restarted while the patient is being treated with systemic corticosteroids except for patients on stable doses of hormone replacement therapy such as hydrocortisone.

6.2.2 Immune-Related Adverse Events (irAEs)Reactions and Immune-mediated Adverse Reactions: Definition, Monitoring, and Treatment

These are suggested guidelines for the management of immune-related adverse events. For the purposes of this study, an immune-related adverse reaction is defined as an adverse reaction of unknown etiology associated with drug exposure and consistent with an immune phenomenon. Efforts should be made to rule out neoplastic, infectious, metabolic, toxin or other etiologic causes prior to labeling an event an irAEs. Serologic, immunologic, and histologic (biopsy) data should be used to support the diagnosis of an immune-related toxicity. Suspected immune-related adverse reactions must be documented on an AE or SAE form. Another term for an irAE is an immune-mediated adverse reaction, as it is termed in the Ipilimumab US Prescribing Information. Both terms may be used in this protocol document.

Patients should be informed of and carefully monitored for evidence of clinically significant systemic immune-mediated adverse reactions (e.g., systemic lupus erythematosus-like diseases) or organ-specific immune-mediated adverse reaction (e.g., rash, colitis, uveitis, hepatitis or thyroid disease). If an immune-mediated adverse reaction is noted, appropriate work-up (including biopsy if possible) should be performed, and steroid therapy may be considered if clinically necessary.

It is unknown if systemic corticosteroid therapy has an attenuating effect on ipilimumab activity. However, clinical anti-tumor responses have been maintained in patients treated with corticosteroids and discontinued from ipilimumab. If utilized, corticosteroid therapy should be individualized for each patient. Prior experience suggests that colitis manifested as \geq grade 3 diarrhea requires corticosteroid treatment.

Suggested guidelines for specific immune-mediated adverse reactions are included in [section 6.4](#) below, in [Appendix C](#), and the package insert. These suggested guidelines should be utilized as clinically appropriate for the treatment of individual patients. Please contact the overall PI or drug monitor for any questions.

Overview of Management of Immune Related AE

Immune related AE include dermatologic, gastrointestinal, hepatic, endocrine and other less common inflammatory events that resolve from general immunologic enhancement. Temporary

immunosuppression with corticosteroids, tumor necrosis factor-alpha antagonists, mycophenolate mofetil, or other agents can be effective treatment in most cases.

For patients with moderate or severe immune related AE, this requires interruption of the ipilimumab and the use of corticosteroid immunosuppression. Treatment is based upon the severity of the observed toxicity:

- For patients with grade 2 (moderate) immune-mediated toxicities, treatment with ipilimumab should be withheld and should not be resumed until symptoms or toxicity is grade 1 or less. Corticosteroids (prednisone 0.5 mg/kg/day or equivalent) should be started if symptoms do not resolve within a week.
- For patients experiencing grade 3 or 4 (severe or life-threatening) immune-mediated toxicities, treatment with ipilimumab should be permanently discontinued. High doses of corticosteroids (prednisone 1 to 2 mg/kg/day or equivalent) should be given. When symptoms subside to grade 1 or less, steroids can be gradually tapered over at least one month.

6.3 Other Guidance for the Treatment of Ipilimumab Associated Reactions

The following guidance is provided for the management of ipilimumab treatment related events. These suggested guidelines, treatment algorithms in [Appendix C](#), and further information in the investigator's brochure, should be considered in the context of appropriate medical treatment for each patient.

6.3.1 Treatment of Infusion Reactions Associated with Ipilimumab

Since ipilimumab contains only human protein sequences, it is less likely that any allergic reaction will be seen in patients. However, it is possible that infusion of ipilimumab will induce a cytokine release syndrome that could be evidenced by fever, chills, rigors, rash, pruritus, hypotension, hypertension, bronchospasm, or other symptoms. No prophylactic pre-medication should be given unless indicated by previous experience in an individual patient. Reactions should be treated based upon the following recommendations.

- For mild symptoms (e.g., localized cutaneous reactions such as mild pruritus, flushing, rash):
 - Decrease the rate of infusion until recovery from symptoms, remain at bedside and monitor patient.
 - Complete the ipilimumab infusion at the initial planned rate.
 - Diphenhydramine 50 mg IV may be administered at the discretion of the treating physician and patients may receive additional doses with close monitoring.
 - Premedication with diphenhydramine may be given at the discretion of the investigator for subsequent doses of ipilimumab.
- For moderate symptoms (any symptom not listed above [mild symptoms] or below [severe symptoms] such as generalized pruritus, flushing, rash, dyspnea, hypotension with systolic BP >80 mmHg):
 - Interrupt ipilimumab.
 - Administer diphenhydramine 50 mg IV.

- Monitor patient closely until resolution of symptoms.
- Corticosteroids may abrogate any beneficial immunologic effect, but may be administered at the discretion of the treating physician.
- Resume ipilimumab infusion after recovery of symptoms.
- At the discretion of the treating physician, ipilimumab infusion may be resumed at *one half the initial infusion rate, then increased incrementally to the initial infusion rate.*
- If symptoms develop after resumption of the infusion, the infusion should be discontinued and no additional ipilimumab should be administered that day.
- The next dose of ipilimumab will be administered at its next scheduled time and may be given with pre-medication (diphenhydramine and acetaminophen) and careful monitoring, following the same treatment guidelines outlined above.
- At the discretion of the treating physician additional oral or IV antihistamine may be administered prior to dosing with ipilimumab.
- For severe symptoms (e.g., any reaction such as bronchospasm, generalized urticaria, systolic blood pressure <80 mm Hg, or angioedema):
 - Immediately discontinue infusion of ipilimumab, and disconnect infusion tubing from the subject.
 - Consider bronchodilators, epinephrine 1 mg IV or subcutaneously, and/or diphenhydramine 50 mg IV, with solumedrol 100 mg IV, as needed.
 - Patients should be monitored until the investigator is comfortable that the symptoms will not recur.
 - No further ipilimumab will be administered.
- In case of late-occurring hypersensitivity symptoms (e.g., appearance within one week after treatment of a localized or generalized pruritus), symptomatic treatment may be given (e.g., oral antihistamine, or corticosteroids).

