 - At the time of response assessments, patients with evidence of disease progression will come off study unless they have evidence of clinical benefit (i.e. improvement in transfusion frequency or peripheral blast reduction). Patients with evidence of disease progression may be allowed to stay on study if deriving clinical benefit with approval from the overall PI as there may be a delayed response with immunotherapy.
 - Additional maintenance dosing (following the same schedule of ipilimumab dosed on day 1 every other cycle with monthly decitabine) for patients with clinical benefit at completion of maintenance therapy will be considered with Overall PI until progression or unacceptable toxicity.

Regimen Description					
Agent	Premedications; Precautions	Dose	Route	Schedule	Cycle Length
Decitabine	Anti-emetic agent per institutional guidelines (i.e. compazine 10 mg injection or equivalent as slow push at a rate not to exceed 5 mg/min per institutional standards given 30 minutes [+/- 15 minutes] prior to chemotherapy)	20 mg/m ² (reconstituted and mixed per institutional guidelines)	Recommend giving decitabine first prior to ipilimumab. IV over 60 minutes [+/- 15 minutes].	Days 1-5 every 4 weeks	
Ipilimumab	None unless history of prior reaction Please see section 6.3 for recommendations for hypersensitivity precautions	1, 3 (starting dose level), 5, or 10 mg/kg	IV over 90 minutes (not bolus or IV push) [+/- 15 minutes]. Administer after decitabine infusion is completed (any time within four hours after infusion completion).	Day 1* every 4 weeks during induction and every 8 weeks during maintenance	28 days (4 weeks)

*Ipilimumab does not start until cycle 1

Please also refer to [section 6](#) for dose delay guidelines.

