5.4 General Concomitant Medication and Supportive Care Guidelines

Growth factor support is not routinely recommended for low blood counts unless there is a concern for severe sepsis, septic shock or persistent infection (e.g. fungal infection) per institutional standards. Transfusion support is allowed, and can be used at the discretion of the investigators. Prophylactic antibiotics can be utilized as appropriate for disease or as needed in the post allo-HCT setting at the discretion of the investigators.

Suggested hypersensitivity precautions with ipilimumab: In the event of a hypersensitivity reaction, stop infusion, notify MD/NP/respiratory and pharmacy, administer oxygen as needed, monitor vital signs and proceed with administering hypersensitivity medications as needed. Medications to consider having available for hypersensitivity precautions:

Suggested medications for hypersensitivity precautions:

- Diphenhydramine 25-50mg IV as needed (begin with 25 mg, if continued reaction then administer additional 25 mg)
- Methylprednisolone or equivalent 40mg IV once as needed,
- Meperidine injection 12.5-25mg IV as needed for rigor/fever and/or chills during hypersensitivity reaction (start with 12.5 mg). If patient has continued reaction, administer additional 12.5 mg.
- Acetaminophen tablet 650 mg (oral) as needed for fever; hold if given already as a premedication
- Famotidine 20mg/50mL in NS IVPB or equivalent as needed for hypersensitivity; hold if already given as premedication
- Epinephrine IM injection 0.3mg as needed for anaphylaxis; may administer every 5 minutes up to 3 doses)
- Please refer to institution specific hypersensitivity reaction treatment algorithm for more clinical support

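### Sections 5.4 and 6.3.1 give different epinephrine doses and routes for a severe or anaphylactic reaction to ipilimumab, and nothing says which prevails

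*Combined protocol and SAP*

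**What the plan says.** Section 5.4 opens its guidance with "Suggested hypersensitivity precautions with ipilimumab: In the event of a hypersensitivity reaction, stop infusion, notify MD/NP/respiratory and pharmacy". It then lists medications, without grading the reaction by severity. Three entries matter here:

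- Epinephrine: "Epinephrine IM injection 0.3mg as needed for anaphylaxis; may administer every 5 minutes up to 3 doses".
- Steroid: "Methylprednisolone or equivalent 40mg IV once as needed".
- Diphenhydramine: "Diphenhydramine 25-50mg IV as needed (begin with 25 mg, if continued reaction then administer additional 25 mg".

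The list ends with "Please refer to institution specific hypersensitivity reaction treatment algorithm for more clinical support".

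Section 6.3.1 covers infusion reactions to ipilimumab in three tiers: mild, moderate and severe. The severe tier begins "For severe symptoms (e.g., any reaction such as bronchospasm, generalized urticaria, systolic blood pressure <80 mm Hg, or angioedema" and, after telling staff to end the infusion, continues: "Consider bronchodilators, epinephrine 1 mg IV or subcutaneously, and/or diphenhydramine 50 mg IV, with solumedrol 100 mg IV, as needed". The introduction to section 6.3 describes its content as suggested guidance, to be weighed in the context of each patient's care.

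The Regimen Description table in section 5.1, in the ipilimumab cell for premedication and precautions, says: "Please see section 6.3 for recommendations for hypersensitivity precautions". It does not mention section 5.4.

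**The concern.** A protocol may leave the choice of rescue drug to the treating physician. It should not state two different doses by two different routes for one drug in one situation without saying which applies. An infusion unit that draws on the protocol, whether for an order set or for reference, will find one epinephrine instruction in section 5.4 and another in section 6.3.1. Staff who have read one section have no signal that the other exists. The event is an acute one that leaves little time to compare sections, so the matter is one of patient safety. The steroid and diphenhydramine entries raise the same question less sharply.

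**Working it through.** No statistical figure is involved, so the check sets the two sections side by side.

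| Item | Section 5.4 | Section 6.3.1, severe tier |
|---|---|---|
| Trigger | Any hypersensitivity reaction to ipilimumab; the epinephrine line is for anaphylaxis | Severe symptoms during or after the infusion, with four example signs |
| Epinephrine | 0.3 mg IM, 5-minute intervals, at most 3 doses | 1 mg IV or subcutaneous, no repeat rule |
| Steroid | Methylprednisolone or equivalent, 40 mg IV, once | Solumedrol 100 mg IV |
| Diphenhydramine | Start at 25 mg IV, a further 25 mg if the reaction continues | 50 mg IV |
| Institutional algorithm | Mentioned | Not mentioned |

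**Do both apply to one event?** Section 5.4 does not define anaphylaxis. If an anaphylactic reaction shows any one of the example signs in the severe tier (bronchospasm, widespread urticaria, angioedema, or systolic pressure under 80 mm Hg), it meets both triggers. It might be said that section 6.3.1 deals with cytokine release and section 5.4 with allergy. But section 6.3.1 names signs typical of hypersensitivity, goes on to late hypersensitivity symptoms, and is where the section 5.1 table sends readers for hypersensitivity precautions. The protocol itself treats both sections as covering this ground.

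**Epinephrine.** The stated amounts are 0.3 mg and 1 mg, and 1 / 0.3 = 3.3. That ratio only describes the printed figures: it compares milligrams across different routes, and the documents give no basis for putting those on one scale. What the text does establish is that the doses differ and that the set of routes in one section (IM) shares no member with the set in the other (IV, subcutaneous). A user cannot comply with both.

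**Steroid.** Taking solumedrol to be methylprednisolone, 100 / 40 = 2.5. The 40 mg entry stands in an ungraded list and the 100 mg entry only in the severe tier, so part of the gap may reflect severity.

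**Diphenhydramine.** The starting doses are 25 mg and 50 mg, but section 5.4 allows 25 + 25 = 50 mg in total. This is a difference in titration. Severity alone does not explain it, because section 6.3.1 names 50 mg in its mild and moderate tiers as well.

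**Is there a rule of precedence?** Neither section cites the other. The section 5.1 table names section 6.3 only. The reference in section 5.4 to the local algorithm offers further support and does not say that the algorithm overrides the listed doses. No other text ranks the two lists.

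**The case against.** The strongest reply is that neither passage is an order. Section 5.4 is headed as suggested and speaks of medications to consider having available. Section 6.3 calls itself guidance, and the severe-tier line begins with an invitation to consider. Section 5.4 also points sites to their own algorithm, which many would follow first. All of this is true, and it means the protocol does not mandate either dose. It does not remove the conflict. Discretion over whether to give epinephrine does not reconcile two doses and routes once the decision to give it is made. Section 5.4 also tells staff to proceed with giving the medications as needed, and section 6.3.1 says that reactions should be treated on the basis of its recommendations. The local algorithm is mentioned in one section only.

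A second reply is that a general list and a severe tier may properly differ. For the steroid this has force, and for diphenhydramine the difference is mainly in how the dose is built up. A reader might infer that all three drugs contradict each other equally for the same severe reaction; the documents do not support that, because two of the three entries in section 5.4 are not tied to severe reactions. For epinephrine the reply fails, since section 5.4 reserves that line for anaphylaxis.

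**Conclusion.** The contradiction is real for epinephrine: 0.3 mg IM against 1 mg IV or subcutaneous, with no cross-reference and no precedence. The steroid and diphenhydramine differences are secondary. The conclusion assumes that an anaphylactic reaction would show at least one sign from the severe tier; the steroid comparison also assumes that solumedrol means methylprednisolone. The point warrants correction on safety grounds and leaves the design and the statistical analysis unchanged.

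Three stronger readings may tempt a reader and should not be adopted:

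- That the section 5.4 maximum, 3 x 0.3 = 0.9 mg, falls short of a one-time 1 mg dose. Section 6.3.1 does not call its dose one-time and gives no repeat rule, so it has no maximum to compare.
- That rescue treatment would add toxicity to the DLT count. Section 5.2 requires an event to be at least possibly related to the combination and has its own rule for infusion reactions. Nothing shows that effects of rescue drugs would be attributed to the combination.
- That the section 5.1 pointer to section 6.3 is wrong. Section 6.3.1 does hold the infusion-reaction content and the rules on premedication after a prior reaction. The pointer is incomplete because it leads past the list in section 5.4.

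**What to change.** The sponsor's clinical and pharmacy teams should reconcile sections 5.4 and 6.3.1 in one of two ways:

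1. State drug, dose, route and repeat rule for a severe or anaphylactic reaction in one section only, and have the other section refer to it.
2. State in both sections that the institutional algorithm governs, and remove the conflicting figures from both.

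The reference to section 6.3 in the section 5.1 table should stay and be made consistent with the reconciled text, adding section 5.4 if that list is kept. If the steroid and diphenhydramine differences are intended to follow severity or titration, the text should say so. Which doses and routes to adopt is for those teams to decide.

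The cost is a wording amendment and a check of any site order sets already built from the protocol.
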